## **9.2 Preexisting Conditions**

In this trial, a preexisting condition (i.e., a disorder present before the adverse event reporting period started and noted on the pretreatment medical history/physical examination form) should not be reported as an adverse event unless the condition worsens or episodes increase in frequency during the adverse event reporting period. Recurrence or progression of tumor will not be regarded as an adverse event.

## **9.3 Procedures**

Diagnostic and therapeutic non-invasive and invasive procedures, such as surgery, should not be reported as adverse events. However, the medical condition for which the procedure was performed should be reported if it meets the definition of an adverse event. For example, an acute appendicitis that begins during the adverse event reporting period should be reported as the adverse event and the resulting appendectomy noted under comments.

## **9.4 Adverse Event Reporting Period**

The adverse event reporting period for this trial begins when the patient receives the first dose of investigational medication and ends 28 days after the patient receives the last dose of his/her study medication regimen for all non-serious adverse events. All serious adverse events will be followed through safety follow-up visits until resolution or return to baseline condition.

All adverse events that occur in trial subjects during the adverse event reporting period specified in the protocol must be reported, whether or not the event is considered treatment-related.

IN ADDITION, any known untoward event that occurs subsequent to the adverse event reporting period that the investigator assesses as possibly related to the investigational medication/product should also be reported as an adverse event.

## **9.5 Seriousness (Gravity) of Adverse Event**

Each adverse event is to be classified by the investigator as SERIOUS (including life-threatening) or NONSERIOUS. This classification of the gravity of the event determines the reporting procedures to be followed.

An adverse event that meets one or more of the following criteria/outcomes is classified as **serious**:

- Death
- Life-threatening (i.e., immediate risk of death)
- Inpatient hospitalization, emergency room visit for a period > 24 hours or prolongation of existing hospitalization
- Persistent or significant disability/incapacity
- Congenital anomaly/birth defect
- Other significant medical hazard. An important medical event that may not result in death, threaten life or require hospitalization may be considered a SAE when, based on appropriate medical judgment, it may jeopardize the subject and may require medical or surgical intervention to prevent one of the outcomes listed above. Examples of such

medical events include allergic bronchospasm, requiring intensive treatment in an emergency room or at home, or convulsions that do not result in inpatient hospitalization.

A **nonserious** event is one that does not meet the criteria described for a serious or life-threatening event. Hospitalization for either elective surgery related to a pre-existing condition (without increase in severity or frequency) or routine clinical procedures that are not the result of an adverse event need not be considered as an AE and therefore are not a SAE. A routine clinical procedure is a procedure occurring during the study period that does not interfere with the study product administration or any of the ongoing protocol specific procedures. If anything untoward is reported during an elective procedure, that occurrence must be reported as an AE or SAE, according to the usual criteria.

### **9.6 Eliciting Adverse Event Information**

The investigator is to report all directly observed adverse events and all adverse events spontaneously reported by the trial subject. In addition, as part of the physical exam and clinical assessment, each trial subject will be questioned about adverse events and symptoms at each clinic visit, following initiation of treatment. The question asked will be "Since your last clinic visit, have you had any health problems?"

### **9.7 Attribution of Causality of Adverse Events**

The investigator will assign an attribution to each AE that occurs. Attribution will be determined according to the criteria specified in CTC 4.0, which is summarized below:

*5-Definite* – The AE is *clearly related* to the treatment.

*4-Probable* – The AE is *likely related* to the treatment.

*3-Possible* – The AE *may be related* to the treatment.

*2-Unlikely* – The AE is *doubtfully related* to the treatment.

*1-Unrelated* – The AE is *clearly not related* to the treatment.

### **9.8 Reporting of Adverse Event**

Adverse events (AE) will be reported to the Thomas Jefferson University IRB and the Data Safety Monitoring Board (DSMB) via Clinical Research Management Office (CRMO) as specified in the TJU Data Safety and Monitoring Plan (Refer to Table).

All unexpected on-site adverse events and serious adverse events (SAE) will be sent to the TJU IRB and the DSMC within 48 hours of first awareness of the event. Fatal adverse events which are unexpected must be reported to the TJU IRB and the DSMB within 24 hours of first awareness of the event. Fatalities not related to the study drug must be reported within 5 days. Quarterly safety updates will be submitted to the CRMO, and the DSMC.

AEs will be reported according the table below:

Unexpected Event:

GRADE 1-3	GRADE 4	GRADE 5
Attribution of Possible, Probable or Definite (as defined in CTC 4.0)	Regardless of Attribution (as defined in CTC 4.0)	Death
Report to CRMO via website within 48 hours. Report to TJU IRB within 48 hours. CRMO reports to DSMC immediately following receipt.	Report to CRMO via website within 48 hours. Report to TJU IRB within 48 hours. CRMO reports to DSMC immediately following receipt.	Report to CRMO via website and TJU IRB within 24 hours.

Expected Event:

GRADE 1-3	GRADE 4	GRADE 5
Attribution of Possible, Probable or Definite (as defined in CTC 4.0)	Regardless of Attribution (as defined in CTC 4.0)	Death
Report to CRMO via website within 10 working days. Summary of all adverse events submitted quarterly to DSMC.	Report to CRMO via website and TJU IRB within 48 hours. CRMO reports to DSMC immediately following receipt. Summary of all adverse events submitted quarterly to DSMC.	Report to CRMO via website and TJU IRB within 5 days. Summary of all adverse events submitted quarterly to DSMC.

## 9.9 Safety Reporting Requirements for IND Holders

In accordance with 21 CFR 212.32, sponsor-investigators of studies conducted under an IND must comply with following safety reporting requirements:

### **Expedited IND Safety Reports:**

#### 7 Calendar-Day Telephone or Fax Report:

The Sponsor-Investigator is required to notify the FDA of any fatal or life-threatening adverse event that is unexpected and assessed by the investigator to be possibly related to the use of *PD-0332991*. An unexpected adverse event is one that is not already described in the Investigator Brochure. Such reports are to be telephoned or faxed to the FDA within 7 calendar days and *Pfizer* within 24 hours of first learning of the event. Each telephone call or fax transmission (see fax number below) should be directed to the FDA new drug review division in the Center for Drug Evaluation and Research or in the product review division for the Center for Biologics Evaluation and Research, whichever is responsible for the review of the IND.

#### 15 Calendar-Day Written Report:

The Sponsor-Investigator is also required to notify the FDA and all participating investigators, in

a written IND Safety Report, of any serious, unexpected AE that is considered possibly related to the use of [PD-0332991](#). An unexpected adverse event is one that is not already described in the Investigator Brochure.

Written IND Safety Reports should include an Analysis of Similar Events in accordance with regulation 21 CFR § 312.32. All safety reports previously filed with the IND concerning similar events should be analyzed. The new report should contain comments on the significance of the new event in light of the previous, similar reports.

Written IND safety reports with Analysis of Similar Events are to be submitted to the FDA, [Pfizer](#), and all participating investigators within 15 calendar days of first learning of the event. The FDA prefers these reports on a MedWatch 3500A Form but alternative formats are acceptable (e.g. summary letter).

FDA fax number for IND Safety Reports:

[name]

All written IND Safety Reports submitted to the FDA by the Sponsor-Investigator must also be faxed to:

[Pfizer](#)

Fax: [[name]]([contact])

Any issues encountered with fax transmission can be reported by calling [name] [contact]

AND:

Thomas Jefferson University IRB

For questions related to safety reporting, contact [name] [contact]

## **IND Annual Reports**

In accordance with the regulation 21 CFR § 312.32, the Sponsor-Investigator shall within 60 days of the anniversary date that the IND went into effect submit a brief report of the progress of the investigation. Please refer to Code of Federal Regulations, 21 CFR § 312.32 for a list of the elements required for the annual report. All IND annual reports submitted to the FDA by the Sponsor-Investigator should be copied to [Pfizer](#).

### **9.9 Recording Instructions**

On the adverse event case report forms, the investigator will use the NCI Common Toxicity Criteria (CTC) version 4.0 ([http:// ctep.info.nih.gov/ CTC3/default.htm](http://ctep.info.nih.gov/CTC3/default.htm)) to describe the maximum intensity of the adverse event. The investigator will also be asked to assess the possible relationship between the adverse event and the investigational medication as well as any concomitant medications.

### **9.10 Expected Adverse Reactions for PD-0332991**

The data described below represent Phase I study (N=74) of PD-0332991 at escalating doses of 25-225 mg/d at either Schedule 3/1 (25-125 mg/d) or Schedule 2/1 (150-225 mg/d). The most common adverse events (regardless of causality) include fatigue (51%), neutropenia (42%),

nausea (35%), anemia (30%), diarrhea (30%), constipation (27%), vomiting (23%), dyspnea (19%), thrombocytopenia (15%), abdominal pain (14%), anorexia (14%), cough (14%), leucopenia (11%), flatulence (11%), peripheral edema (11%), back pain (11%), decreased appetite (10%), and rash (10%). Eleven dose-limiting toxicities, which consisted of neutropenia and/or thrombocytopenia, were observed. Grade 3 adverse events (regardless of causality) included dyspnea (4 subjects), hyperbilirubinemia (1 subject), jaundice (1 subject), acute renal failure (1 subject), hyperglycemia (1 subject), pleural effusion (1 subject), and peripheral sensory neuropathy (1 subject). Grade 4 adverse events (regardless of causality) included neutropenia (2 subjects), anemia (1 subject), thrombocytopenia (1 subject), increase in uric acid (1 subject), hyperglycemia (1 subject), and pulmonary embolism (1 subject).

*Effects on bone marrow:* Based on nonclinical studies performed to date, bone marrow was a target organ for toxicity. In these studies, hematologic and bone marrow abnormalities were reversible after dosing of PD-0332991 ceased. Neutropenia, thrombocytopenia, leucopenia, and anemia have been commonly observed in the clinical program. These events were not cumulative and were reversible, and generally did not result in treatment discontinuation. Granulocyte-colony stimulating factors should not be used prophylactically, but they may be used to treat treatment-emergent neutropenia as indicated by the current ASCO guidelines. Erythropoietin may be used for the supportive treatment of anemia. Complete blood counts with differential should be checked frequently during clinical studies, and dosing of PD-0332991 should be interrupted based on hematologic parameters specified above (Section 8.1).

*Effects on the respiratory tract:* Based on nonclinical studies performed to date, the respiratory tract was a target organ for toxicity. Dyspnea and cough were commonly observed in the clinical program, but were Grade 3 in severity and were attributed to the disease. There was one Grade 4 adverse event of pulmonary embolism, but this event was not considered to be treatment-related.

*Effects on the GI tract:* GI adverse events including abdominal pain, constipation, diarrhea, flatulence, nausea and vomiting were commonly observed in the clinical program. Only those of Grade 1 severity were considered to be attributed to treatment.

### **9.11 Exposure in Utero**

Fertility and teratology studies with PD-0332991 have not been conducted. Safety for women of childbearing capacity cannot be implied from the existing data. Thus, women should avoid becoming pregnant while on therapy, and women of childbearing potential must be apprised of the potential hazard to the fetus, which includes severe malformation (teratogenicity), failure to thrive and fetal death (embryotoxicity).

### **9.12 Follow-Up of Adverse Event**

All adverse events should be followed until they are resolved or the subject's participation in the trial ends. In addition, all serious adverse events and those non-serious events assessed by the investigator as possibly related to the investigational medication/product should continue to be followed even after the subject's participation in the trial is over. Such events should be followed until they resolve or until the investigator assesses them as "chronic" or "stable." Resolution of such events is to be documented on the CRF.

### **9.13 Non-Hematological and Hematological Adverse Events**

Patients will be assessed clinically for toxicity prior to each dose using the National Cancer Institute (NCI) CTCAE Version 4. If patients experience Grade 3 or greater toxicity deemed related to study drug, PD-0332991 will be temporarily discontinued. After the resolution of toxicity to Grade 1 or less, PD-0332991 will be restarted at the initial dose. The study treatment will be continued until disease progression or unacceptable side effects (Grade 3 or greater). Patients with unacceptable side effects (Grade 3 or greater) for a second time on PD-0332991 will be removed from the study. The only exception to this are: Grade 3 anorexia, nausea vomiting, stomatitis/mucositis or diarrhea that will lead to investigational product withdrawal only if not manageable despite maximum supportive care. Throughout the study investigators may prescribe any concomitant medications or treatments necessary to provide adequate supportive care other than experimental or approved anti-tumor therapies. All concomitant medications must be recorded.

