### **5.3 Visit 3 – Toxicity Assessment**

Initial safety and tolerability of the study drug will be assessed after 2 weeks on PD-0332991. The evaluation will include:

1. Clinical assessment – including interval history, physical examination, weight, vital signs, signs/symptoms, and performance status.
2. Toxicity assessment. Adverse events will be graded using the National Cancer Institute (NCI) Common Toxicity Terminology Criteria for Adverse Events v 4.0 (CTCAE v 4.0).
3. Concomitant medication review
4. Blood cell counts (CBC with differential, platelets) and comprehensive chemistries (albumin, alkaline phosphatase, total protein, BUN, creatinine, AST (SGOT), ALT (SGPT), total bilirubin, calcium, sodium, potassium, chloride, bicarbonate), lactate dehydrogenase (LDH).

If subject experiences a Grade 3 or greater toxicity deemed related to study drug, PD-0332991 will be temporarily discontinued. After the resolution of toxicity to Grade 2 or less, PD-0332991 will be restarted at the initial dose. The study treatment will be continued until disease progression or unacceptable side effects (Grade 3 or greater). Subjects with unacceptable side effects (Grade 3 or greater) for a second time on PD-0332991 will be removed from the study. The only exception to this are: Grade 3 anorexia, nausea vomiting, stomatitis/mucositis or diarrhea that will lead to investigational product withdrawal only if not manageable despite maximum supportive care.

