If a subject is not able to tolerate the 75 mg dose, then treatment should be discontinued. If a dose reduction has been performed, the subject may be re-escalated by the treating physician provided toxicities have resolved to Grade 2.

**Table 8.3** outlines the procedures for dose modifications for bone marrow toxicity related to PD0332991.

Due to baseline coagulopathy and tendency to have bleeding events due to underlying liver disease, dose modifications should not be based on hemoglobin values. If a subject experiences bone marrow toxicity of both WBCs and platelets the recommended dose adjustment should be based on WBC count. It is recommended that standard of care be followed for administration of RBCs and platelets and for vitamin K in patients with ESLD.

**Table 8.3** Dose modifications/delays for bone marrow toxicity related to PD0332991

Grade of Event CTCAE v 4.03	Dose Interruption	Dose Modification for Remainder of Cycle.	Dose Modification for Subsequent Cycles
0-2	Treat on time	No change	No change
3-4	
 
• Delay until <math>\leq</math> Grade 2
 
• Administer 6 mg pegfilgrastim (Neulasta) subcut if WBC/ANC does not recover to <math>\leq</math> Grade 2 after 1 week dose interruption
 
	
 
• First episode: No change
 
• Second episode within cycle after co-administration with pegfilgrastim: Reduce 1 dose level
 
	
 
• Continue at dose level from previous cycle
 
• If serious drug-related myelosuppression occurs including: A. febrile neutropenia or B. sepsis with neutropenia, in previous cycle institute permanent dose reduction at -1 dose level
 
• If bone marrow toxicity recurs at <math>\geq</math> Grade 3 with leucocyte growth factor administration then
 

			institute permanent dose reduction at -1 dose level 
 
• If unable to resume PD-0332991 due to BM toxicity for an entire cycle, institute permanent dose reduction at -1 dose level
 
• If bone marrow toxicity remains at <math>\leq</math> Grade 2 for remainder of a previous cycle after administration of pegfilgrastim, then administer with subsequent cycles, 6 mg subcut on day 1 once per cycle
 

--	--	--	---

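### Sections 5.3, 8.4 and 9.13 conflict on restart grade, later-cycle dose and removal after drug-related Grade 3 or greater toxicity

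*Combined protocol and SAP*

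**What the plan says.** Three places in the protocol tell the investigator what to do after a drug-related toxicity of Grade 3 or greater.

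- **Section 5.3** interrupts the drug and then says: "After the resolution of toxicity to Grade 2 or less, PD-0332991 will be restarted at the initial dose". On recurrence: "Subjects with unacceptable side effects (Grade 3 or greater) for a second time on PD-0332991 will be removed from the study". Section 5.4 applies the Visit 3 procedures to later visits, so this rule is not confined to week 2.
- **Section 9.13**, headed for both non-hematological and hematological events, has the same trigger but says: "After the resolution of toxicity to Grade 1 or less, PD-0332991 will be restarted at the initial dose". On recurrence: "Patients with unacceptable side effects (Grade 3 or greater) for a second time on PD-0332991 will be removed from the study".
- **Section 8.4 with Table 8.3** covers bone marrow toxicity. Grade 3–4 events are held until Grade 2 or less, and Grade 0–2 is treated on time. Pegfilgrastim is given if WBC/ANC has not recovered after a one-week interruption. A first episode brings no dose change for the rest of the cycle. A further one is handled so: "Second episode within cycle after co-administration with pegfilgrastim: Reduce 1 dose level". For later cycles the default is the previous cycle's dose, with listed exceptions, one being drug-related "A. febrile neutropenia or B. sepsis with neutropenia, in previous cycle institute permanent dose reduction at -1 dose level". The text before the table adds: "If a subject is not able to tolerate the 75 mg dose, then treatment should be discontinued". It also says that "dose modifications should not be based on hemoglobin values".

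Sections 5.3 and 9.13 share a closed list of exceptions to second-event removal: Grade 3 anorexia, nausea, vomiting, stomatitis/mucositis and diarrhea. Blood counts are not on it.

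**The concern.** For one trigger the sections differ on three things: how far the toxicity must resolve before dosing resumes, what dose is given in later cycles, and whether a patient with a second event stays in the study. Not all of them can be followed.

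The conflict falls on the toxicity most to be expected. Section 1.2 names myelosuppression as the principal dose-limiting toxicity, and Section 9.10 reports that all eleven Phase I dose-limiting toxicities were neutropenia and/or thrombocytopenia. At stake is patient safety (dosing again too early, or at full dose in later cycles after febrile neutropenia) and consistent conduct. Site staff, and the auditors described in Section 15.0, could not tell a compliant decision from a deviation.

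**Working it through.** The plan states no figure to reproduce. The check sets the rules side by side and maps grades to counts.

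**Step 1. The rules compared**

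| Question | 5.3 | 9.13 | 8.4 / Table 8.3 (marrow only) |
|---|---|---|---|
| Restart when resolved to | Grade 2 or less | Grade 1 or less | Grade 2 or less |
| Dose for rest of cycle, first episode | Initial (125 mg) | Initial (125 mg) | No change |
| Later cycles after febrile neutropenia, neutropenic sepsis, or an entire cycle missed for marrow toxicity | Initial (125 mg) | Initial (125 mg) | Permanent level −1 (100 mg) |
| Second Grade 3 or greater marrow event | Removed | Removed | Stays on drug (see Step 4) |

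**Step 2. Restart grade in counts (Table 8.2)**

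| Count | Lowest value allowing restart under 9.13 (Grade 1) | Under 5.3 and Table 8.3 (Grade 2) | Gap |
|---|---|---|---|
| ANC, ×10⁹/L | 1.5 | 1.0 | 0.5 |
| Platelets, ×10⁹/L | 75 | 50 | 25 |
| WBC, ×10⁹/L | 3.0 | 2.0 | 1.0 |

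A patient recovering from Grade 3–4 toxicity to ANC 1.0 to <1.5, platelets 50 to <75 or WBC 2.0 to <3.0 is at Grade 2. That patient restarts under 5.3 and Table 8.3 and stays off drug under 9.13. Section 4.1 allows entry at ANC 1.5 and platelets 75, so under 9.13 a patient who entered at those limits must regain the full baseline value before restarting.

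**Step 3. Dose (Table 8.1).** Level −1 is 100/125 = 80% of standard, and level −2 is 75/125 = 60%. In the later-cycle situations of Step 1, Table 8.3 therefore gives 20% less than 5.3 and 9.13. For a first episode within the current cycle the sections agree.

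**Step 4. Second marrow event.** The branches of Table 8.3 are:
- a second episode in the cycle after pegfilgrastim: down one level;
- recurrence at Grade 3 or greater with growth factor: permanent reduction to level −1;
- otherwise: continue at the previous cycle's level, unless one of the later-cycle conditions in Step 1 applies.

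None of these removes the patient. Treatment stops under 8.4 if 75 mg is not tolerated, and the general withdrawal criteria in Section 5.6 still apply. Under 5.3 and 9.13 the second event is itself the reason for removal.

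**Step 5. Precedence.** Neither 5.3 nor 9.13 refers marrow toxicity to Table 8.3. Section 9.10 points hematologic interruptions to Section 8.1, which is a general drug description with no hematologic parameters. For non-hematological toxicity Table 8.3 does not apply, so nothing decides between Grade 1 (9.13) and Grade 2 (5.3).

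**The case against.** The best defence is that the intended marrow rule can be recovered. Table 8.3 is specific to marrow toxicity, Section 9.10 points to Section 8 even if to the wrong subsection, and 5.3, Table 8.3 and the re-escalation rule in 8.4 all use Grade 2, which leaves 9.13 as the outlier. This is a fair guess at intent. But the heading of 9.13 names hematological events, no available text gives Table 8.3 priority, and 5.3 agrees with 9.13, not with Table 8.3, on second-event removal. The defence also leaves the non-hematological restart grade open.

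Practical safeguards exist. This is a single-institution study, the Sponsor-Investigator must approve dose adjustments (8.4), and 5.4 leaves removal for an adverse event to clinical judgment. These reduce the chance of harm but supply no rule, and they sit beside mandatory wording in 5.3 and 9.13.

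A reader might infer more than the text supports on four details:
- **That Table 8.3 always lowers the dose at a second event.** It does so after pegfilgrastim or growth factor, or under the other later-cycle conditions. A second platelet-only episode, or a neutropenia that recovers within a week, gets no automatic reduction.
- **That intolerance of 75 mg is the sole stopping point under Table 8.3.** Section 5.6 also withdraws for unacceptable toxicity and for less than 50% of the required dose over two consecutive cycles.
- **That the sections differ on dose immediately after febrile neutropenia.** The reduction stands in the column for subsequent cycles.
- **That 9.13 imposes a hemoglobin target of 10 g/dL on patients admitted at 8 g/dL.** This follows only if 9.13 is read alone. Section 8.4 largely answers it, though it does not say whether holds are covered as well as dose changes.

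**Conclusion.** The conflict is real and the text is wrong as written. After drug-related Grade 3 or greater marrow toxicity, a patient whose count is in the Grade 2 band is on or off drug depending on the section followed. After a second such event, the patient is removed under 5.3 and 9.13 or remains on treatment under Table 8.3. In three defined situations the later-cycle dose is 125 mg or 100 mg. For non-hematological toxicity the restart grade is unresolved between 5.3 and 9.13.

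The size can be given only as these differences in rule. The documents give no frequency of such events at 125 mg in HCC. The eleven Phase I events come from 74 subjects across 25–225 mg/d on two schedules and do not serve as a rate. The time from Grade 2 to Grade 1 recovery is not stated, so the dose lost to longer holds cannot be calculated.

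A reader might infer that the conflict alters who is counted in the TTP analysis, because Section 11.1 requires two cycles and a week 8 assessment and replaces those not evaluable. The documents do not establish this. A patient with two marrow events and holds before week 8 might fall short of two cycles under Table 8.3 as well. Section 11.1 also says that efficacy endpoints are estimated for all subjects.

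The verdict rests on the text available. A short part of Section 8.4, between Table 8.2 and the text leading to Table 8.3, was not available. It could bear on how Section 8.4 relates to other sections, but it could not make the restart grades in 5.3 and 9.13 agree.

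**What to change.** 1. In both 5.3 and 9.13, state that bone marrow toxicity (hold, restart, dose reduction and discontinuation) follows Section 8.4 and Table 8.3, including the hemoglobin rule, and is exempt from the initial-dose restart and second-event removal rules. Say whether the hemoglobin rule covers holds.
2. Have the sponsor choose one restart grade for non-hematological toxicity and use it in both sections. The documents do not show which grade was intended.
3. In 9.10, change the cross-reference from Section 8.1 to Section 8.4 (Table 8.3).

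The cost is a wording amendment to three sections, one clinical decision, and the IRB review that Section 13.2 requires for amendments. No tests, visits or patients are added.
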